#### 4.2.8. Missing, Unused, and Spurious Data

All data recorded on the CRF will be included in data listings that will accompany the clinical study report.

For the primary efficacy endpoint and other success/failure secondary endpoints, subjects who discontinue prior to Week 12 will be considered treatment failures, a worst-case scenario.

These endpoints include

- Clinical Remission (primary endpoint)
- Clinical Response
- Endoscopic Response
- Endoscopic Remission

A single sensitivity analysis on each of these endpoints will utilize the per protocol population (complete-case) in order to examine the robustness of the results.

For all continuous secondary endpoints, data will be analyzed using a mixed model repeated measures approach described in Section 4.6.2. The MMRM method assume that missing data arose from a missing at random (MAR) mechanism, i.e. the missing data is independent of unobserved data given the non-missing data. The MAR assumption is reasonable in clinical trials as the observed data explain much of the missingness in many scenarios, particularly in well controlled studies such as clinical trials, in which an extensive effort is made to observe all the outcomes and the factors that influence them. In MMRM, the information from the observed data is used via the within-patient correlation structure to provide information about unobserved data. The data from all visits are simultaneously analyzed using restricted maximum likelihood methods and no explicit imputation for missing values is performed. This method will be used in the testing of the secondary endpoints.

In addition, sensitivity analyses may be performed on complete datasets where missing data is imputed using the following methodology:

- LOCF (last observation carried forward)
- WOCF (missing data imputed using the worst observation observed prior to that time point)
- Per Protocol population (complete-case scenario- no imputation required)
- Multiple Imputation

For multiple imputation, two approaches may be used. In the first approach, for missing response data at various time points, the following steps are taken:

- Draw a random sample from the normal distribution with a mean and variance calculated from the non-missing responses at that time point
- Repeat this process five times to form five imputed complete datasets
- Fit the MMRM model to each imputed dataset to estimate the treatment effect on the response variable and the variance

- Combine the results from the five imputed dataset using SAS Proc MIANALYZE to derive the multiple imputation estimates of treatment effect and variance.

The second multiple imputation approach will be used to impute data in the event that missing data are missing not at random (MNAR) but rather depend on the observed and unobserved data. This imputation approach would use the same steps as above, but the random sample would be drawn from a distribution pre-defined and related to the responses that are observed.

Exploratory endpoints will not be imputed.

Adverse event (AE) dates that are missing or incomplete will be handled in the following manner to determine whether an AE is treatment-emergent:

If the start date/time of an AE is partially or completely missing, the date/time will be compared as far as possible with the date/time of the start of administration of study drug. The AE will be assumed to be treatment emergent if it cannot be definitively shown that the AE did not occur or worsen during the treatment-emergent period (worst case approach).

The following general rules will be used:

- If the start time of an AE is missing but the start date is complete, an AE will only be excluded as being treatment emergent if the start date is before the date of study drug administration or if the stop date/time is before study drug administration.
- If the start time and day are missing but the start month and year are complete, an AE will only be excluded as being treatment emergent if the start month/year is before the month/year of study drug administration or if the stop date/time is before study drug administration.
- If the start day and month are missing but the start year is complete, an AE will only be excluded as being treatment emergent if start year is before the year of study drug administration or if the stop date/time is before study drug administration.
- If the start date is completely missing, an AE will be considered treatment-emergent unless the stop date/time is before study drug administration.

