5.3 Removal of Subjects from Study Participation

In accordance with the Declaration of Helsinki and other applicable regulations, a subject has the right to withdraw from the study at any time and for any reason without prejudice to his or her future medical care by the physician or at an institution. The Investigator (or designee) may remove a subject from the study if, in the Investigator's (or designee's) opinion, it is not in the best interest of the subject to continue the study. Subjects may be withdrawn due to (but not limited to) any of the following:

- change in compliance with inclusion/exclusion criterion that is clinically relevant and affects subject safety
- at the subject's request (withdrawal of consent)
- protocol noncompliance
- occurrence of AEs that, in the Investigator's opinion, require subject removal
- occurrence of pregnancy
- intake of non-permitted concomitant medication that might affect subject safety or study assessments/objectives.

Notification of withdrawal will be made to the Sponsor as soon as is practical. In case of withdrawal, all reasonable efforts will be made to perform all final study day assessments within 10 days of termination (eg, Early Termination visit) ([Table 6-1](#)). The date the subject is withdrawn from the study and the reason for withdrawal will be recorded on the subject's Case Report Form (CRF). All withdrawn subjects will be followed until resolution of all their AEs or until the unresolved AEs are judged by the Investigator (or designee) to have stabilised.

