6.3.2 Concomitant Medications

Subjects will refrain from participation in any other investigational study drug trial in which receipt of any investigational drug occurred within 5 half-lives or 1 month, whichever is longer, prior to Screening and during the entire study.

Subjects will be expected to continue their existing medication regimen, provided those treatments are permitted in the protocol.

Subjects may be receiving the following drugs at enrolment and must maintain stable doses throughout the treatment and follow-up period:

- Oral 5-ASA therapy may be continued provided that subjects have been on treatment for at least 6 weeks with a stable dose for the 2 weeks immediately prior to screening endoscopy
- Oral corticosteroid therapy (prednisone at a stable dose ≤ 20 mg/day, or equivalent steroid) may be continued provided that subjects have been on treatment for at least 4 weeks with a stable dose for at least 2 weeks immediately prior to screening endoscopy
- Azathioprine or 6-MP may be continued provided that the dose has been stable for the 4 weeks immediately prior to screening endoscopy
- Antidiarrhoeals (eg, loperamide, diphenoxylate with atropine) may be continued at a stable dose for control of chronic diarrhoea

- Probiotics (eg, Culturelle, *Saccharomyces boulardii*) may be continued provided that the dose has been stable for the 2 weeks immediately prior to screening.

The following drugs must be discontinued and may not be used during the study:

- Use of topical 5-ASA or corticosteroid enemas/suppositories must be discontinued within 2 weeks prior to the screening endoscopy
- TNF- α antagonist drugs must not be used within 60 days prior to screening
- Ustekinumab must not be used within 3 months prior to screening
- Cyclosporine, thalidomide, tacrolimus, sirolimus, or mycophenolate mofetil must not be used within 1 month prior to screening
- Investigational drugs or biologic agents must not be used within 1 month (or 5 half-lives) prior to screening
- Vedolizumab, natalizumab, or other biologic therapy must not be used during the study. Subjects with prior treatment with vedolizumab or natalizumab are not eligible for participation in the study.
- No live viral vaccines should be administered within 1 month prior to screening
- Subjects must have discontinued antibiotics for treatment of infection according to the criteria listed in [Section 5.2](#).

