6.8 Final Treatment Day Clinical Site Visit (Day 84 or Early Termination)

The following assessments should be performed:

- AEs
- concomitant medications
- weight
- vital signs
- 12-lead ECG
- complete physical examination
- clinical laboratory evaluations (including haematology, coagulation, serum chemistry [fasting], CRP, and UA; see [Appendix B](#))
- PML subjective checklist (see [Appendix D](#)); any positive responses to the PML subjective checklist will require that the PML objective checklist be performed by the Investigator according to [Appendix D](#) and the study manual
- serum pregnancy test (WOCBP)
- sigmoidoscopy and biopsy
- complete Mayo Score assessment (rectal bleeding, stool frequency, PGA, and endoscopy subscores; see [Appendix A](#))
- IBDQ (see [Appendix G](#))

- faecal calprotectin
- PK blood sample (within 1 hour prior to dosing and 1, 2, and 4 hours \pm 20 minutes postdose)
- PD blood sample (within 1 hour prior to dosing and 4 hours \pm 20 minutes postdose; at selected sites only)
- ADA testing

Subjects who experience a flare of UC requiring rescue treatment that is prohibited in the protocol (in the judgement of the Investigator) will be discontinued from further treatment with study drug. Subjects who terminate early from treatment may be placed on appropriate therapy by the treating physician. Subjects will complete an Early Termination visit (including endoscopy) within 10 days following discontinuation, undergo the study procedures detailed in the Study Flow Chart ([Table 6-1](#)), and will be encouraged to be followed for all safety assessments through 28 days.

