Multiplicity will be addressed via closed testing procedure with combined p-values computed for each of the 2 stages of the trial (IA and post-IA). Each stage p-value will be adjusted as appropriate by closed testing multiple comparison approach per Simes.²⁴ This approach controls the overall type 1 error at $\alpha=0.025$, 1-sided.

All analyses will be based on combined Stage 1 and Stage 2 data and include data from the dose(s) that is (are) dropped for Stage 2. Exploratory analyses will be carried out to assess consistency of results between Stages 1 and 2. Analyses of other binary endpoints will be carried out similarly.

Subjects who discontinue prematurely will be considered treatment failures.

Changes from baseline complete Mayo Score, partial Mayo Score, rectal bleeding subscore, stool frequency subscore, endoscopic subscore, IBDQ score, and faecal

calprotectin levels will be analysed using repeated measures mixed analysis of covariance model adjusted for treatment, time point, treatment-by-time point interaction, stratification factors, and baseline values. For subjects who withdraw prematurely, the last observation will be carried forward. These analyses will be based on the Stage 1 and Stage 2 combined data for exploratory purposes.

Details regarding the statistical analyses of efficacy data will be provided in the Statistical Analysis Plan (SAP).

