## 2.5. Efficacy, Pharmacokinetic, and Safety Variables

### 2.5.1. Efficacy Variables

The primary efficacy endpoint for this study is the proportion of subjects receiving PTG-100 with clinical remission at Week 12 compared with placebo.

Clinical remission is defined as follows using the Mayo subscores of stool frequency, rectal bleeding, and endoscopy:

1. Stool frequency subscore of 0 or 1 with a pre-specified change of 1 or more from baseline
2. Rectal bleeding subscore of 0
3. Endoscopy subscore of 0 or 1 (modified so that a score of 1 does not include friability)

Secondary endpoints, all based on comparison of individual PTG-100 dose levels with placebo, include:

1. Proportion of subjects with clinical response at Week 12 (Day 84) (defined as at least 1 point and 30% reduction from baseline in rectal bleeding and stool frequency subscores)
2. Proportion of subjects with endoscopic response at Week 12 (Day 84) (defined as an endoscopic subscore of 0 or 1)
3. Mean change in endoscopy subscore from baseline to Week 12 (Day 84)
4. Mean change in rectal bleeding subscore from baseline to Weeks 2, 4, 6, 8, 10, 12, and 16 (Days 14, 28, 42, 56, 70, 84, and 112)
5. Mean change in stool frequency subscore from baseline to Weeks 2, 4, 6, 8, 10, 12, and 16 (Days 14, 28, 42, 56, 70, 84, and 112)
6. Proportion of subjects with endoscopic remission at Week 12 (defined as an endoscopic subscore of 0)
7. Mean change in Complete Mayo Score (including all four subscores) from baseline to Week 12 (Day 84)
8. Mean change in Partial Mayo Score (excluding endoscopy subscore) from baseline to Weeks 2, 4, 6, 8, 10, 12, and 16 (Days 14, 28, 42, 56, 70, 84, and 112)
9. Mean change in fecal calprotectin levels from baseline to Weeks 6 (Day 42) and 12 (Day 84)
10. Mean change in IBDQ score from baseline to Week 12 (Day 84)

Exploratory endpoints include:

1. Mean change in histological score from baseline to Week 12
2. Effects of ADA on PK, safety, and efficacy in subjects with positive ADA

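### Only discontinuers are scored as failures, so a subject who adds or raises UC medication and stays to Week 12 can be counted as a remitter

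*SAP*

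**What the plan says.** **Failure rule.** SAP 4.2.8 states that "subjects who discontinue prior to Week 12 will be considered treatment failures, a worst-case scenario". It applies this to clinical remission, clinical response, endoscopic response and endoscopic remission. Protocol 7.4 agrees: "Subjects who discontinue prematurely will be considered treatment failures".

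**Endpoint.** SAP 2.5.1: "Clinical remission is defined as follows using the Mayo subscores of stool frequency, rectal bleeding, and endoscopy". Neither SAP 2.5.1 nor Protocol 7.4 attaches a condition on concomitant or rescue medication.

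**Background therapy.** Protocol 6.3.2: "Subjects may be receiving the following drugs at enrolment and must maintain stable doses throughout the treatment and follow-up period". The list covers oral 5-ASA, oral corticosteroids, azathioprine/6-MP, antidiarrhoeals and probiotics. A second list opens "The following drugs must be discontinued and may not be used during the study"; it does not name a raised dose of any drug on the first list. New or as-needed medication is to be documented in the source records and the CRF.

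**Stopping and withdrawal.** Protocol 6.8 stops study drug for "Subjects who experience a flare of UC requiring rescue treatment that is prohibited in the protocol", as judged by the investigator. Protocol 5.3 gives reasons for which a subject may be withdrawn, among them protocol noncompliance and "intake of non-permitted concomitant medication that might affect subject safety or study assessments/objectives".

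**Other analyses.** SAP 4.8.5 tabulates and lists concomitant medications. SAP 4.2.8 and 4.6.1 repeat the binary analyses in the Per Protocol population. Under SAP 3.2, exclusions from that population are at the sponsor's discretion, decided before unblinding and final before hard database lock.

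**The concern.** The protocol tells sites that background UC doses must not change, but neither document says how a breach is scored. If a subject's steroid is raised at Week 6, the subject completes Week 12 and the three subscores qualify, the plan as written records a remission for the assigned arm. The background drug may have produced it.

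At stake is what the primary proportion measures. Without a rule it mixes remission on assigned treatment with remission reached after added therapy, and the mix can differ between arms. More escalation on placebo raises the placebo rate and dilutes the effect. More escalation on active inflates the effect and can produce a false positive. Clinical response, endoscopic response and endoscopic remission have the same gap.

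**Working it through.** **1. Follow each type of subject through the text.**

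| Subject before Week 12 | Governing text | Score in the FAS |
|---|---|---|
| Flare; investigator judges that prohibited rescue is needed; study drug stopped | Protocol 6.8, then the failure rule | Failure, if stopping study drug counts as discontinuing |
| Takes a prohibited UC drug but is not withdrawn | Protocol 5.3 (withdrawal optional) | As observed |
| Raises oral steroid, 5-ASA or azathioprine/6-MP and continues | Protocol 6.3.2 (breach; no analysis consequence) | As observed |
| Newly starts a permitted UC drug and continues | Protocol 6.3.2 (documented in the CRF) | As observed |

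The first row is not fully secure: neither document says whether *discontinue* in the failure rule means leaving study drug or leaving the study.

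**2. Reproduce the plan's power.** Protocol 7.1 and SAP Table 2 state 91% at N=240 for true rates 0.10/0.20/0.31/0.31, 82% for 0.10/0.17/0.24/0.31, and 2.2% under the null, at one-sided 0.025. I simulated two stages with 40,000 runs, the Simes closed test and inverse-normal combination with w1 = sqrt(n1/N). Assumed because not stated: unstratified pooled z-tests, and the two doses with most Stage 1 remitters kept.

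- Stage 1 of 60, no overrun: 90.5%, 80.8%, 1.8%.
- Stage 1 of 80, no overrun: 89.9%, 80.6%, 1.8%.
- Stage 1 of 60 with the 60-subject overrun spread over four arms: 88.4%, 78.3%, 1.7%.

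The stated power is not in dispute.

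**3. One dose against placebo, illustrative inputs.** From the documents: rates of 10% and 31%, one-sided 0.025, 70 to 80 per selected group. Assumed, with no source in the documents: 5-10% of placebo and 2.5-5% of active subjects escalate, and 30% of those become remitters because of it.

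Counted rates:
- Lower case: 0.10 + 0.05 × 0.30 = 0.115; 0.31 + 0.025 × 0.30 = 0.3175.
- Upper case: 0.10 + 0.10 × 0.30 = 0.13; 0.31 + 0.05 × 0.30 = 0.325.

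Power = Φ{[d√n − 1.96√(2p̄(1−p̄))] / √(p1(1−p1)+p2(1−p2))}, where d = p2 − p1 and p̄ is the mean of p1 and p2. For 0.10 against 0.31 at n = 70: (0.21 × 8.367 − 1.96 × 0.5709)/0.5513 = 1.157, and Φ = 0.876.

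| Counted rates | n = 70 | n = 80 |
|---|---|---|
| 0.10 / 0.31 | 88% | 92% |
| 0.115 / 0.3175 | 84% | 88% |
| 0.13 / 0.325 | 79% | 84% |

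**4. Sensitivity to direction, two-stage simulation at N=240.** The 91% scenario is the base for the power rows. The first figure is for Stage 1 of 60 with overrun; the second is for Stage 1 of 80 without.

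| Added to counted remission | Result |
|---|---|
| Nothing | power 88% / 90% |
| 2 points, placebo only | power 78% / 80% |
| 5 points, placebo only | power 59% / 60% |
| 10 points, placebo only | power 27% / 28% |
| 5 points, every arm | power 82% / 84% |
| 2 points, active arms only, true null | false positives 4.6% (first layout), against 1.7% |
| 5 points, active arms only, true null | false positives 13.2% (first layout) |

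The one-arm rows are extremes. They show that the result is sensitive in both directions, not what is likely.

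**The case against.** **Protocol 6.8 may already cover this.** Raising a steroid to treat a flare breaks the stable-dose rule and can be read as prohibited rescue. The subject would then stop study drug and be scored a failure. This stands in part. The wording allows that reading but does not require it, it rests on the investigator's judgement, and it does not reach a subject who stays on study drug after a breach.

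**A check already exists.** The primary analysis is repeated in the Per Protocol population, with violations reviewed before unblinding, and medication use is listed. This also stands in part. Medication changes are not named as major violations, exclusion is discretionary, and an excluded subject leaves the denominator instead of counting as a failure. The FAS result is unaffected.

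**Scoring completers as observed is a recognised choice.** True, but the plan does not state it as a choice for subjects with changed medication. It already uses a failure rule for discontinuers, and 6.3.2 treats stable background therapy as a condition of the trial.

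**Stronger readings the documents do not support.** A reader might infer that *worst-case* in SAP 4.2.8 is a false label. It describes how discontinuers are imputed, and for them it is accurate. A reader might also infer that escalation must be commoner on placebo, so that the effect is necessarily diluted. No document gives an escalation rate for any arm. Nor is 79% the trial's power: it comes from assumed rates and a single fixed comparison, not the combination test.

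**Conclusion.** The gap is real and lies in the text. Discontinuation is the only trigger for imputed failure. A subject who adds or raises UC therapy, or takes a prohibited UC drug, and remains to Week 12 is analysed as observed on all four binary endpoints. Protocol 6.8 narrows the gap to an extent that depends on how prohibited rescue is read, and the per-protocol analysis may remove some of these subjects; neither closes it in the primary analysis.

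The size and direction of any bias are unknown. The figures above rest on assumed escalation rates and show only that a few points of imbalance between arms would matter. The conclusion does not depend on them: it needs only that some subjects breach the stable-dose or prohibited-drug rules and stay in. The documents do not show that the protocol permits escalation, or that every rescued subject would be counted as a remitter. The rule should be settled before unblinding.

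**What to change.** **SAP 4.2.8.** For the four binary endpoints, also classify as a non-remitter or non-responder any subject who, before the Week 12 assessment, starts a prohibited UC therapy, or newly starts or increases above baseline an oral corticosteroid, oral 5-ASA or azathioprine/6-MP.

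**Qualifying list.** Fix it under blind review of the concomitant-medication data before unblinding. It must say how antidiarrhoeal changes are handled, since these can act directly on stool frequency, and how trivial or transient changes are handled. A blanket rule on any increase would turn one extra antidiarrhoeal or probiotic dose into a failure.

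**Sensitivity analysis.** Keep the analysis of observed status regardless of medication, so that the effect of the rule can be seen.

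**Record and reconcile.** Enter the change in SAP section 5, which now reports none. The sponsor should reconcile Protocol 5.3, 6.3.2 and 6.8 on what counts as prohibited rescue, and state whether discontinuation means leaving study drug or leaving the study.

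**Cost.** SAP wording, a blinded review of data already being collected, and slightly lower observed remission rates. Only outcome classification changes, not what patients may receive.

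### The optional multiple imputation ignores arm and earlier data, and the only sensitivity analysis for remission equates complete-case with the per protocol set

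*SAP*

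**What the plan says.** SAP 4.2.8 analyses the continuous secondary endpoints with a mixed model for repeated measures (MMRM) under missing at random (MAR). Its stated reason is: "In MMRM, the information from the observed data is used via the within-patient correlation structure to provide information about unobserved data".

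It then lists sensitivity analyses that may be performed: last observation carried forward (LOCF), worst observation carried forward (WOCF), the per protocol (PP) population, and multiple imputation.

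- **First imputation.** "Draw a random sample from the normal distribution with a mean and variance calculated from the non-missing responses at that time point", then "Repeat this process five times to form five imputed complete datasets", then "Fit the MMRM model to each imputed dataset to estimate the treatment effect on the response variable and the variance". No conditioning variable is named.
- **Second imputation, for data missing not at random (MNAR).** The steps are the same, except that "the random sample would be drawn from a distribution pre-defined and related to the responses that are observed". The SAP gives no distribution, shift or reference arm.

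For remission, clinical response, endoscopic response and endoscopic remission, subjects who stop before Week 12 count as failures. The one sensitivity analysis for each endpoint "will utilize the per protocol population (complete-case) in order to examine the robustness of the results". The list for continuous endpoints uses the same label: "Per Protocol population (complete-case scenario- no imputation required".

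SAP 3.1 defines PP as the full analysis set (FAS) less subjects with major protocol violations. The FAS needs a dose, a baseline result and at least one post-baseline result. Neither set requires Week 12 data.

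**The concern.** A sensitivity analysis should change the missing-data assumption in a known direction and leave the rest alone. Two of those planned do not.

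The MMRM is justified because a subject's own earlier data inform the missing value. The first imputation discards those data and, as written, also discards the arm. Its estimate could differ from the MMRM's because of how the draws were made, with no information about dropout. The MNAR version cannot be run from the text.

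For remission, the rule to be tested is that discontinuation equals failure. That is the least favourable value for each subject, but not necessarily for the comparison: if placebo subjects stop more often, it favours PTG-100. A reader needs to know how far the result depends on the rule, and the PP analysis does not isolate that.

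**Working it through.** The plan states no figure on this point, so there is none to reproduce.

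**Inputs.** From the documents: five imputations and the draw rule (SAP 4.2.8); 70 to 80 subjects per selected arm (protocol 7.2), taken as 75; remission of about 10% on placebo with a difference of about 21 points (protocol 7.1). Assumed, because the documents give none: 10% to 30% missing, SD 1, true Week 12 difference 0.50, correlation 0.6 between an earlier visit and Week 12.

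**1. Pooled draws, closed form.** Let m0 and m1 be the observed means on placebo and active, f0 and f1 the missing fractions, arms of equal size, and w = (1 − f1)/[(1 − f0) + (1 − f1)] the active share of observed subjects. The pooled mean is M = m0 + w(m1 − m0). The expected difference after imputation is

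(1 − f1)m1 + f1·M − (1 − f0)m0 − f0·M = (m1 − m0)·[1 − f1 + w(f1 − f0)].

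When f0 = f1 = f this is (1 − f)(m1 − m0). The shrinkage applies to the observed difference whatever caused the dropout. Data missing completely at random (MCAR) do not rescue it.

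- f = 0.10: 0.9 × 0.50 = 0.45
- f = 0.20: 0.8 × 0.50 = 0.40
- f = 0.30: 0.7 × 0.50 = 0.35
- f0 = 0.20, f1 = 0.10: w = 0.9/1.7 = 0.529; 0.50 × (0.9 − 0.0529) = 0.42

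Simulation under MCAR with five draws recovered 89%, 80%, 70% and 85% of the true difference, against 90%, 80%, 70% and 85% by formula.

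**2. Dropout driven by an earlier visit (MAR).** The earlier visit has an arm difference of 0.3. The probability of dropout is 1/(1 + exp(c + 1.2 × earlier value)), with c = 2.6, 1.6 and 1.0. There were 4,000 datasets per row, and the true difference is 0.50.

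| Missing, placebo / active | Pooled draws | Draws by arm | Using arm and earlier visit |
|---|---|---|---|
| 11% / 8% | 0.43 | 0.48 | 0.50 |
| 22% / 17% | 0.38 | 0.47 | 0.50 |
| 31% / 26% | 0.34 | 0.47 | 0.51 |

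The last column uses regression predictions, which is enough to check bias. Other settings of the dropout model put draws by arm between 0.46 and 0.48.

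In the middle scenario the correlation between the earlier visit and Week 12 on placebo fell from 0.60 to 0.36 after pooled draws, and was about 0 among the imputed values. This is the correlation that the MMRM relies on.

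The estimates are differences in means. In completed data, the MMRM's Week 12 contrast is essentially that difference adjusted for baseline and stratum, so the shrinkage carries over.

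**3. Complete-case against PP.** Take two FAS subjects.

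- A stops at Week 6 with no major violation. A is in PP by SAP 3.1 and has no Week 12 data. A remains a failure in a PP analysis but would leave a true complete-case analysis.
- B has all Week 12 components and a major violation. B is out of PP but would stay in a complete-case analysis.

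The two sets differ in both directions, so the statement that no imputation is needed does not follow. SAP 4.6.1 describes the repeat of the primary analysis on PP without the complete-case label.

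**4. Why the failure rule deserves its own check.** Near the design rates, take 23/75 against 8/75. The pooled rate is 31/150 = 0.2067, the standard error is √(0.2067 × 0.7933 × 2/75) = 0.0661, and z = 0.200/0.0661 = 3.02. If five placebo subjects counted as failures were really remitters (13/75), the pooled rate is 36/150 = 0.24, the standard error is 0.0697, z = 0.1333/0.0697 = 1.91 and one-sided p = 0.028, above 0.025. Five is 7% of the arm. This is an extreme allocation in a simple single-stage test. It shows only what a tipping-point analysis would measure.

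**The case against.** The SAP does not say that the draws are pooled over arms; it is silent. A competent programmer might draw by arm, and the bias would then be small. That stands, and both readings are shown above. It does not rescue the rule: draws by arm assume MCAR within arm, which is stronger than MAR.

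The stakes are limited, and this also stands. The imputation is optional, serves only continuous secondary endpoints, and errs toward no effect. In the MCAR simulation the 95% intervals from pooled draws still covered the truth in 94% to 96% of datasets, so the harm is an attenuated estimate. A reader might infer that all the missing-data sensitivity analyses fail, or that a false positive could result. The documents support neither. LOCF and WOCF use each subject's own data and are untouched by this criticism.

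A reader might also infer that the failure rule for remission is never varied. The parenthetical label could mean PP subjects with observed Week 12 data, and some discontinuers may leave PP as violators, since SAP 3.2 leaves exclusions to the sponsor. On that reading the rule is varied, but mixed with removal of violators. The fault is a label that contradicts its definition, not a proven absence of any check.

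Finally, protocol 6.8 takes subjects with a flare needing prohibited rescue off study drug. For them failure is arguably the outcome and not an imputation. That is a fair limit on whom a tipping-point analysis should cover.

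**Conclusion.** The point holds in two parts, and both should be corrected before unblinding.

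First, the imputation rule is wrong as written. It shrinks the difference by about the missing fraction if pooled. If done by arm it loses about 4% to 8% (0.46 to 0.48 against 0.50) under MAR dropout driven by an earlier visit. On neither reading does it stress the MMRM's assumption. The proportional shrinkage under pooling with equal missingness needs no assumption about SD or effect; the other figures rest on the assumed dropout, effect and correlation. The MNAR alternative is not specified enough to run.

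Second, the only sensitivity analysis for remission and the other binary endpoints does not isolate the discontinuation-equals-failure rule. This is the part that touches the primary endpoint. The documents do not show that the primary conclusion would change.

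**What to change.** In SAP 4.2.8:

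1. Impute by arm, or with arm in the model, from prior anti-TNF stratum, baseline and the available earlier visits. The endoscopy subscore, complete Mayo score and IBDQ are scheduled only at baseline and Day 84 or Early Termination, so use earlier partial Mayo scores as auxiliary data for these.
2. Write down the MNAR distribution, for example reference-based on placebo or a stated range of delta shifts.
3. Define complete-case as FAS subjects with all Week 12 components observed, and report it separately from PP.
4. Add a tipping-point analysis of remission over subjects with missing Week 12 data, by arm. State which discontinuers count as failures by definition and which as missing.
5. Reconcile SAP 4.6.2, which carries the last observation forward in the main continuous analysis, with 4.2.8, which says that nothing is explicitly imputed there.

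The cost is SAP wording, standard imputation code and a few more tables. No data collection or sample size changes. More than five imputations would be a reasonable preference, but it is secondary.
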